## **16. Health Information and Privacy Compliance**

MEDICAL PROTOCOL (HRP-590)

PROTOCOL TITLE: Magnesium sulfate as adjuvant analgesia and its effect on opiate use by post-operative transplant patients in the pediatric ICU.

VERSION DATE: 06/09/2022

16.1. Select which of the following is applicable to your research:

I am requesting that all research participants sign a HIPCO approved HIPAA Disclosure Authorization to participate in the research (either the standalone form or the combined consent and HIPAA Authorization).

Appropriate Use for Research: Per language in the consent at initial procedural discussions with the surgeon, unless consenting to enroll for magnesium analgesia, patients will not be involved in any research protocol. MRN's will not be forwarded to IDS or protocol team to initiate any form of data collection or medication administration.

16.2. Identify the source of Private Health Information you will be using for your research (Check all that apply)

I will pull records directly from EPIC.

16.3. Explain how you will ensure that only records of patients who have agreed to have their information used for research will be reviewed: Patients who have consented for the study will have their information shared with the research team. Patient information is updated in RedCap. Only patients enrolled in study will have RedCap entries, which will be the only patients whose Epic charts will be accessed for further data collection.

16.4. Approximate number of records required for review: 60 retrospective records (30 liver transplant, 30 TPIAT), 30 prospective. Informatics consulting service will be utilized, however certain data may require more thorough progress note analysis and therefore direct epic access from data reviewer.

16.5. Please describe how you will communicate with research participants during the course of this research. Check all applicable boxes

Communication with research participants will take place in the course of treatment, through MyChart, or other similar forms of communication used with patients receiving treatment. Specifically, communication will happen throughout their PICU course regarding their overall care, which will include discussions on analgesia and sedation to ensure these are optimized (this happens during family-centered rounds on all patients admitted to the PICU).

16.6. Explain how the research team has legitimate access to patients/potential participants:

## MEDICAL PROTOCOL (HRP-590)

PROTOCOL TITLE: Magnesium sulfate as adjuvant analgesia and its effect on opiate use by post-operative transplant patients in the pediatric ICU.

VERSION DATE: 06/09/2022

Members of the research team are also part of the PICU team involved in patient care, and therefore will have access to medical records independent of this project (PI is a PICU attending physician, co-investigators are transplant surgeon and PICU fellow physician). A medical student will also be assisting in data collection as part of their research experience. All members have been confirmed to have completed appropriate HIPAA and research training through UMN standards. Access to patient charts is discussed during the consent process with patients. A number of data points require manual searching in epic. None of these data points require demographic or personalized information outside of sex, age, and strictly medical information (name and contact information are ignored for example).

16.7. Location(s) of storage, sharing and analysis of research data, including any links to research data (check all that apply).

In the data shelter of the [Information Exchange \(IE\)](#)

Store  Analyze  Share

In the Bone Marrow Transplant (BMT) database, also known as the HSCT (Hematopoietic Stem Cell Transplant) Database

Store  Analyze  Share

In REDCap (recap.ahc.umn.edu)

**Store**  Analyze  Share

In Qualtrics (qualtrics.umn.edu)

Store  Analyze  Share

In OnCore (oncore.umn.edu)

**Store**  **Analyze**  Share

In the University's Box Secure Storage (box.umn.edu)

Store  Analyze  Share

In an AHC-IS supported server. Provide folder path, location of server and IT Support Contact:

Store  Analyze  Share

In an AHC-IS supported desktop or laptop.

Provide UMN device numbers of all devices:

Store  Analyze  Share

## MEDICAL PROTOCOL (HRP-590)

PROTOCOL TITLE: Magnesium sulfate as adjuvant analgesia and its effect on opiate use by post-operative transplant patients in the pediatric ICU.

VERSION DATE: 06/09/2022

Other. Describe:

Indicate if data will be collected, downloaded, accessed, shared or stored using a server, desktop, laptop, external drive or mobile device (including a tablet computer such as an iPad or a smartform (iPhone or Android devices) that you have not already identified in the preceding questions

- I will use a server not previously listed to collect/download research data
- I will use a desktop or laptop not previously listed
- I will use an external hard drive or USB drive ("flash" or "thumb" drives) not previously listed
- I will use a mobile device such as an tablet or smartphone not previously listed

*16.8. Consultants. Vendors. Third Parties. N/A*

*16.9. Links to identifiable data: MRN's will be uploaded securely into RedCap, there will be no other links or substitute identifiers required.*

*16.10. Sharing of Data with Research Team Members. Data will be stored via RedCap and OnCore programming only.*

*16.11. Storage and Disposal of Paper Documents: There are no anticipated paper products other than signed consent/assent forms, which will be stored in a secure, locked storage box in co-investigator's fellow office on UMN Children's Hospital grounds.*

## **17. Confidentiality**

*17.1. Data Security: All members of the investigation team will complete and maintain university standard training programs regarding patient information protection, including all modules provided at initiation of fellowship. As stated, this will be extended to medical student researcher involved with assistance in chart review. Protocol, study schedule, and patient enrollment will be tracked via OnCore. Various outcome measures collected from the Epic EMR will be transferred to REDCap storage system. Both of these are HIPAA compliant. This system is password-protected and encrypted for security. Consent forms will be stored in patients' medical chart, with the purpose of easy retrieval and access for PICU medical staff to initiate the intervention following transfer from operating room. This will be reflected in the confidentiality section of the consent form. Paper copies of consent/assent forms will be stored in a secure, locked storage box in co-investigator's fellow office on UMN Children's Hospital grounds.*

## **18. Provisions to Monitor the Data to Ensure the Safety of Participants**

## MEDICAL PROTOCOL (HRP-590)

PROTOCOL TITLE: Magnesium sulfate as adjuvant analgesia and its effect on opiate use by post-operative transplant patients in the pediatric ICU.

VERSION DATE: 06/09/2022

*18.1. Data Integrity Monitoring:* The PI and co-investigators will be in direct day-to-day contact (specifics below) throughout the study intervention and with any of the following that arise. The PI and/or co-investigator will have direct notifications any time a transplantation surgery is planned and will confirm that study intervention has been ordered correctly in medical chart on day of PICU admission. Surgery, anesthesia, ICU, and safety monitoring teams will be notified prior to interventions when a patient is confirmed as a study participant. Medical staff will be instructed to page PI and/or co-investigators as well as research coordinator in case of any intervention side effect for further direction. The PI and co-investigators are the most appropriate direct monitors, as both have full understanding of research protocol, and are also frequently in PICU with direct care of these patients. In cases where the PI or co-investigators are not present, deferral will be made to the medical team, which is already adept and required to be following lab results and ensuring nurse orders are carried out. A co-investigator will also otherwise make routine daily lab surveillance for added layer of monitoring. This level of monitoring appears appropriate as once the intervention is ordered in our EMS, nurses carry out the order throughout duration of study. There is no blinding required in this study as all participants will be intended to receive intervention, so there appears no opportunity for bias introduced by the PI or co-investigators while caring for these patients. As patients complete their ICU and conclude their involvement in study, chart reviewer will be notified to update data into REDCap. This will be further overseen by PI and co-investigators. All data collected through chart review will be collected with a standardized data collection form to ensure uniformity.

Specific safety measures to prevent protocol non-compliance include the following: study team will have a brief after enrollment of each patient and prior to infusion initiation to review pertinent protocol elements, which will be debriefed to medical team (both in email and in person); a study team member will check-in with medical team and bedside nursing team twice per day to ensure compliance and answer any questions; a study team member will check in at major checkpoints (specifically at dosing change and at discontinuation); there will be a request for nursing to be calling study team at medication discontinuation for added layer of safety; a study member will be available for contact from care providers at all times; only study team members are able to direct order changes in epic pertaining to MgSO4 dose or frequency of level checks, resident physicians specifically are not to change these orders (medical team attending or fellow physicians may change dosing per protocol if level > 3.5 mg/dL); study team will additionally contact both bedside nursing team and medical team following completion of infusion to review current safety profile (specifically lab trends, infusion dosing, appropriateness of timing, and active problem list to ensure no adverse events secondary to MgSO4). In regards to OR

## MEDICAL PROTOCOL (HRP-590)

PROTOCOL TITLE: Magnesium sulfate as adjuvant analgesia and its effect on opiate use by post-operative transplant patients in the pediatric ICU.

VERSION DATE: 06/09/2022

safety, a study staff member will be specifically in-hospital on the day of procedure. This staff member will go to the OR every 2 hours at the time magnesium levels are drawn to provide a helpful reminder of blood draw requirement, ask if there are any questions regarding the study drug, and help address any new concerns. Data regarding magnesium levels (and all labs) as well as intra-operative vitals (such as heart rate and blood pressures) and medication deliveries/changes are auto-populated into the patient's electronic medical record in real-time. We do not anticipate that the anesthesia team should have to report any additional data for the study team to help guide dosing magnesium dosing adjustments. The study team member will follow up the result of this level. If there is a needed dosing change based on the level, that study team member will return to the OR to provide a helpful reminder to change the dose (in the case this has not yet been done). If the anesthesia provider is too busy to draw a level or change the dose, which is not anticipated, study team will seek out an available anesthesiologist (i.e. on call provider) to come pause the infusion until able to further discuss. If a study staff member is not forecast to be available for day of procedure, that patient will be excluded from consent. If a study staff member becomes unavailable on day of procedure, that patient will be removed from the study.

A data integrity monitor (external to the direct research team) will be involved throughout this project. The study monitor will ensure that the investigation is conducted according to protocol design and regulatory requirements. The monitor will provide ongoing monitoring of data validity and regulatory issues (e.g. eligibility determinations, consent form process, SAE reporting, IRB actions, disclosures of conflict of interest).

Study records will be monitored at regular intervals by the study monitor. The monitor will perform source data verification and as such must be given access to the participant's primary source documentation, such as paper or electronic medical records, consent to participate in the study, visit dates, demographic information, medical history, physical examination, vital signs, copies of laboratory reports, AEs, concomitant medications, drug accountability (etc.), that support data entries in the REDCap database.

The PI will be provided copies of monitoring reports shortly after the monitoring visit. Findings will be noted and followed up in the subsequent monitoring visit.

The study will be monitored by CTSI in accordance with its institutionally approved monitoring plan.

## MEDICAL PROTOCOL (HRP-590)

PROTOCOL TITLE: Magnesium sulfate as adjuvant analgesia and its effect on opiate use by post-operative transplant patients in the pediatric ICU.

VERSION DATE: 06/09/2022

18.2. Data Safety Monitoring: The following safety data will be collected starting at the baseline visit through the end of study visit to establish any change from baseline parameters, and for monitoring adverse events:

- Confirm that participant met inclusion/exclusion criteria
- Confirm that delivered magnesium dose is appropriate with intended protocol dosing (i.e. 50 mg/kg bolus, 15 mg/kg/hr infusion)
- hypotensive events: including value and interventions needed (pressors, fluid bolus, etc)
- respiratory decline: specifically if needing to increase to higher level of support (nasal cannula to high flow, high flow to positive pressure, etc), interventions required for respiratory compromise, relation to sedation
- arrhythmia: include type, EKG results (if done), interventions required
- hypocalcemia: specifically if ionized calcium < 4 (or age-appropriate norm), interventions required
- hyperkalemia: include value (if higher than normal range), interventions required
- hyperphosphatemia: include value (if higher than normal range), interventions required
- hypermagnesemia: include if > 3.5, confirm that dose was decreased per protocol guideline
- for all of above, comment on whether side effects deemed secondary to magnesium

Safety data will be captured in the CRFs for each visit. Any AEs and SAEs will also be recorded in the REDCap database. Any safety event meeting the IRB's urgent reporting criteria will be reported to the IRB within its published timelines, and similarly to the FDA as outlined at conclusion of this section.

A pediatric ICU physician external to the research team will serve as the safety monitor for this protocol. The safety monitor will not be enrolling any research participants or caring for patients as part of this protocol. The safety monitor is qualified to review the patient safety data generated by this study because of her/his expertise in pediatric intensive care.

After the first 3 patients have completed their study duration, the safety monitor will be responsible for reviewing adverse events and participant data for any clinically significant trends, followed by providing a short one page summary regarding findings. Safety data collected will include the above list, as well as any other unforeseen events which are deemed potentially secondary to magnesium. As long as meeting safety

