### 4. Study Intervention(s)/Investigational Agent(s)

4.1. Description: MgSO4 is a pharmacological agent which will be administered intravenously as a 30-minute bolus dose of 50 mg/kg (maximum 2 grams) in the OR, followed by a 15 mg/kg/hr IV infusion for an additional 48 hours or once the patient has transferred out of the PICU, whichever comes first. The bolus will be given after anesthesia induction for TPIAT patients, and after reperfusion of the transplanted liver for liver transplant patients (this is deemed by surgeon to pose less hemodynamic risk). Of note, it is not anticipated that our patient population would leave the PICU prior to 48 hours. Standard bolus dosing of MgSO4 in pediatrics is 25-75 mg/kg, so per the above literature search 50 mg/kg seems a confirmed safe dosing. Similar dosing protocols using a bolus and infusion which have been studied for analgesia in children without side effect in the literature include the following: 50 mg/kg then 15 mg/kg/hr (18,20), 30 mg/kg then 10 mg/kg/hr (14,25), 50 mg/kg then 8 mg/kg/hr (17). Our proposed 50 mg/kg + 15 mg/kg/hr infusion dose has been utilized effectively and safely at the adult level as well (5,49). Dosing as high as 100 mg/kg then 40 mg/kg/hr has been used in tetanus. To our knowledge, MgSO4 for analgesia remains 'off-label' use, unless discussing for headache pain (used commonly in emergency room medication 'cocktails' for migraines). It is known however that magnesium acts antagonistically on the NMDA receptor, a common nociceptor, one also targeted by ketamine (1). MgSO4 will be delivered at concentration of 100 mg/mL via patient's central line (placed in all transplants regardless of study intervention). MgSO4 is also a physiologically vital electrolyte in the human body, and one that is replaced frequently in the ICU, including in the post-operative transplant population. To avoid nearing toxic magnesium levels, we will titrate medication dosing to be below 3.5 mg/dL. Total magnesium level will be checked in the OR following bolus dose, every 2 hours throughout the transplant procedure, at the initial PICU transfer and every 4 hours [expected window +/- 1 hour] for the remainder of infusion. Other electrolytes (including potassium, ionized calcium, phosphorus) will be checked at least daily (sometimes more if deemed appropriate for other standard of care transplant requirements, which is typically every 6 hours). If any magnesium level is above target, infusion dose will be decreased by 5 mg/kg/hr. These adjustments are based on pharmacokinetic-pharmacodynamic data and pharmacist expertise at the UMN. If magnesium infusion is at any time decreased to 0 mg/kg/hr based on these levels, it will not

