#### 5.2. Study Procedures:

Experimental Group: There will be no operative procedures per study parameters (though the transplantation procedure itself as well as any secondary procedures from complications are otherwise per standard of care). Patient's medical record will be reviewed for basic eligibility criteria (history of myasthenia gravis or heart block). If female and of reproductive age, patient will have a urine B-hCG, which is routine prior to any abdominal surgery. The only prospective study procedure will be the magnesium protocol previously outlined, where IV MgSO4 will be delivered as a 30-minute bolus dose of 50 mg/kg (maximum 2 grams) in OR followed by a 15 mg/kg/hr infusion initiated immediately after (i.e. in OR as well) until conclusion of PICU stay or 48 hours, whichever comes first. Magnesium levels will be monitored throughout the duration of the infusion per above - every 2 hours in OR starting after bolus dose, then every 4 hours [expected window +/- 1 hour]. There are no other baseline visits or follow-up visits independent of the PICU stay and initial consent process. We do not anticipate this study intervention impacting workflow significantly, as infusion medications are standard interventions in the PICU, and these patients already have frequent blood draws. A study schedule with these interventions will be created via OnCore program to ensure compliance with protocol. Data outcomes will be collected from epic EMR at the conclusion of each patient's ICU admission by co-investigator and medical student researcher and stored in REDCap. All collected data is via EMR, so no surveys/scripts/forms are needed for data collection. Specifically, the EMR will be accessed for appropriate transplant patient, followed by selecting the appropriate surgical encounter (which would be current), followed by selecting only specific portals in Epic EMR where intended data elements are located (for example: Intake/Output section, or results review -> magnesium level, etc). Only specific data collection pathways will be targeted while in a patient's medical chart. There are no other drugs/devices involved in study or that would alter MgSO4 delivery. Similarly, there are no out-of-hospital prescriptions or interference during the ICU admission which would alter the study protocol. Any out-of-hospital contact (i.e. pre-admission consent if performed) will include adherence to COVID precautions per hospital guidelines.

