### Control Group:

1. Any patient who had filed as research-exempt (opt-out of research previously).
2. Age less than 3 years or greater than 18 years at transplantation.
3. Any patient with preoperative creatinine level > 1.5x upper limit of normal.

8.3. Screening: No specific screening measures will be used. Any transplant patient will be considered eligible if not pregnant. All consent/recruitment for the study is at same time as transplant procedural consent, which is performed by the transplant surgeon (whom is also a Co-Investigator on this study).

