### ***SIDE EFFECTS AND MISCELLANEOUS***

#### Magnesium variables

1. Magnesium levels
  - average daily level (for each post-operative day), average total level
  - peak level during admission
2. Dosing
  - # of magnesium infusion dosing changes (i.e. # times decreased)
  - total days on magnesium (POD# at discontinuation)
  - # times held due to adverse event concern
  - # of adverse events deemed secondary to magnesium
  - type of adverse event
3. OR Effect
  - Time spent bradycardic (value and %)
  - Overall OR time
  - Fluid requirement
  - Blood product requirement
  - Pressor variables (# required, peak doses)
4. Other effects
  - ionized calcium levels – average daily level (for each post-operative day) and average total level
  - potassium levels – average daily level (for each post-operative day) and average total level
  - phosphorous levels - average daily level (for each post-operative day) and average total level

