## MEDICAL PROTOCOL (HRP-590)

PROTOCOL TITLE: Magnesium sulfate as adjuvant analgesia and its effect on opiate use by post-operative transplant patients in the pediatric ICU.

VERSION DATE: 06/09/2022

outcomes (total days on IV opioids, number of PCA demands and deliveries, number of infusion dose escalations, number of ileus events, days until first stool, emesis counts, number of days naloxone infusion required, PICU duration, number of days intubated, paravertebral block dose increases), categorical outcomes (ketamine use, presence of side effects), and continuous outcomes (FLACC, Pain Score). Longitudinal measurements of magnesium, other analgesics, ionized calcium, PTH, and creatinine levels will be analyzed using mixed effects models. Group summaries including means, standard deviations, and rates will be reported and group differences will be summarized as incidence rate ratios, odds ratios, or mean differences with 95% confidence intervals. Analyses will be conducted using the intent-to-treat principle; control group participants who underwent magnesium replacement (for hypomagnesemia or pre-designed post-transplant protocol) will be included in the control group, and experimental group participants with discontinuation of magnesium, if any, will be included in the experimental group. A two-sided 5% level result will be regarded as significant. Statistical analysis will be per statistician's updated STATISTICAL ANALYSIS SOFTWARE (also used in a previous pain study with TPIAT cohort).

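### Section 18.2 promises change from baseline, but no pre-operative laboratory value is planned for the dataset, and the creatinine and ionized calcium models compare non-randomised cohorts without a baseline term

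*Combined protocol and SAP*

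**What the plan says.** Section 18.2 (Data Safety Monitoring) collects safety data "starting at the baseline visit through the end of study visit to establish any change from baseline parameters". Section 5.2 (Study Procedures) states: "There are no other baseline visits or follow-up visits independent of the PICU stay and initial consent process". Section 8.3 (Screening) adds: "No specific screening measures will be used".

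The first magnesium level that the protocol requires comes after dosing has begun. Section 4.1 has: "Total magnesium level will be checked in the OR following bolus dose, every 2 hours throughout the transplant procedure". Potassium, ionized calcium and phosphorus are to be checked at least daily, and no draw before the bolus is named.

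Section 15.1 takes magnesium as "average daily level (for each post-operative day), average total level", plus a peak. Ionized calcium, potassium and phosphorus are recorded in the same averaged form, and creatinine as daily and total averages. No pre-operative value is listed for any of them.

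Section 15.3 states: "Longitudinal measurements of magnesium, other analgesics, ionized calcium, PTH, and creatinine levels will be analyzed using mixed effects models". The only adjusting covariates named anywhere in 15.3 are transplant type, age and gender. The comparator is a retrospective cohort (section 5.1).

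One pre-operative laboratory value is already used in both cohorts. Section 8.2 excludes, from each group, "Any patient with preoperative creatinine level > 1.5x upper limit of normal".

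**The concern.** There are two separate gaps.

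The first is internal consistency. Section 18.2 states a purpose, change from baseline, that the listed data cannot serve. The protocol neither defines a baseline nor lists a field that would hold one.

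The second is confounding. The laboratory models compare treated children with historical controls. If the cohorts differ before surgery in renal function or calcium, part of that difference carries into the estimated effect of magnesium. Such differences are plausible from the plan itself. Section 8.2 lets the investigator exclude experimental patients on safety or data-quality grounds, with no matching criterion for controls. Section 5.1 leaves the experimental cohort unbalanced by transplant type, while controls are 30 and 30. Transplant type is adjusted for, but section 19.1 says that comorbidities and transplant indication will not be identified in either group, so no other listed variable stands in for pre-operative status. Omitting a correlated baseline also costs precision.

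Section 15.4 has the master data matrix and identification key destroyed at completion, so a field omitted now may be hard to recover later.

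**Working it through.** **The passages side by side**

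| Need | What the plan provides |
|---|---|
| A baseline time point for 18.2 | No visit beyond consent and the PICU stay (5.2); no specific screening measures (8.3) |
| A pre-dose magnesium level | First required level follows the bolus (4.1, 5.2) |
| A pre-operative laboratory field | None in 15.1 |
| Pre-operative creatinine | Needed for eligibility in both cohorts (8.2), not carried into 15.1 |
| A baseline term in the laboratory models | None named in 15.3 |

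Section 15.1 mentions an attachment with the data measures. It is not part of the documents, but 15.1 describes it as the same measures in list form.

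**Which models are affected.** Section 15.3 names magnesium, ionized calcium, PTH and creatinine. Section 15.1 restricts PTH to renal patients, and 15.2 says renal transplants were removed. Magnesium is expected to differ because one group receives a bolus and infusion. That leaves creatinine and ionized calcium. Potassium and phosphorus are collected but not named for mixed models.

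**The plan's own figure.** The only power calculation (15.2) is for opioid dose. With SD 8.3 mg/kg, two-sided 5% and 90 per group, a two-sample t-test gives a detectable difference of 3.49 mg/kg at 80% power, as stated. No laboratory figure is given, and this point does not change the table.

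**Size for a laboratory value.** Inputs from the plan: 30 treated, 60 controls, two-sided 5%. Assumed: pre-operative gap g of 0.1 to 0.5 SD, slope b of post-operative on pre-operative value of 0.3 to 0.7, and, for precision, a correlation ρ over the same range.

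Standard error of the group difference = √(1/30 + 1/60) = 0.224 SD.

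Bias without a baseline term = b × g. False-positive rate = P(|Z + bg/0.224| > 1.96):

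| Gap (SD) | Slope 0.3 | Slope 0.5 | Slope 0.7 |
|---|---|---|---|
| 0.1 | 5.2% | 5.6% | 6.1% |
| 0.2 | 5.8% | 7.3% | 9.6% |
| 0.3 | 6.9% | 10.3% | 15.6% |
| 0.5 | 10.3% | 20.1% | 34.7% |

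Example: g = 0.3 and b = 0.5 give a bias of 0.15 SD; 0.15/0.224 = 0.67; rate 10.3%.

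Detectable difference at 80% power for a single post-operative value = (1.96 + 0.84) × 0.224 × √(1 − ρ²):

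- no baseline: 0.63 SD
- ρ = 0.3: 0.60 SD
- ρ = 0.5: 0.54 SD
- ρ = 0.7: 0.45 SD

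**The case against.** The strongest reply is that 18.2 and 15.3 serve different ends. The 18.2 list supports the safety monitor's review of treated children. Its laboratory items are threshold events (ionized calcium below 4, potassium or phosphorus above normal range, magnesium above 3.5) that need no change score, and creatinine is not among them. This stands. A reader might infer that the 18.2 wording makes the 15.3 analysis defective. It does not, because 15.3 never promises change from baseline; its weakness is the missing covariate.

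A reader might also take these models to be the trial's safety comparisons. They are only some of them. Section 15.1 also collects bradycardia time, pressors, fluids, blood products, adverse events attributed to magnesium and respiratory escalations. The halting rules do not depend on the laboratory models.

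Nor is change from baseline impossible to obtain. Section 5.2 says magnesium is checked independently of the study, and laboratory results enter the record automatically (18.1). The values may well exist; no step extracts them. The adverse-event rules in section 18 also record abnormalities at screening as preexisting conditions, but that captures clinical status, not a laboratory covariate.

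The size can fairly be called assumption-driven. The shared creatinine exclusion, the same surgeon and any adjustment for transplant type, age and gender would limit the gap, and the calculation treats the comparison as otherwise unadjusted. The precision figures are for one post-operative value, not a repeated-measures model. These limits apply to the numbers. They do not supply the missing baseline.

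**Conclusion.** The point holds with limited scope. The 18.2 wording conflicts with 5.2 and with the 15.1 list and needs correcting. Separately, the creatinine and ionized calcium comparisons between non-randomised cohorts should carry a baseline term, and for creatinine the value must already be looked up in both cohorts.

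The false-positive range, from just over 5% to about 35%, rests wholly on an assumed gap of 0.1 to 0.5 SD and slope of 0.3 to 0.7, and no single figure in it is a prediction. The gain in detectable difference, from 0.63 SD to between 0.60 and 0.45 SD, likewise rests on the assumed correlation. The primary opioid analysis is untouched. For magnesium, a false-positive argument has little meaning.

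One further reading should be resisted: that a pre-operative value would give each child's change due to magnesium. Section 4.1 gives liver recipients the bolus only after reperfusion, so their change from the pre-operative value also reflects surgery.

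**What to change.** - **15.1:** for both cohorts, add the last Epic value before the operation for creatinine and ionized calcium, and for magnesium, potassium and phosphorus where available. This definition means the same thing in controls, who had no study bolus.
- **15.3:** add the matching pre-operative value as a covariate in the creatinine and ionized calcium mixed models, and in the magnesium model where available, alongside transplant type, age and gender.
- **18.2:** replace the reference to a baseline visit with this definition. State that for liver recipients the change from the pre-operative value also reflects surgery, so the adjusted between-cohort difference, not the within-patient change, estimates the magnesium effect.

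The cost is up to five chart fields per child and one covariate per model, with no new draw and no change to treatment. Some pre-operative values will be missing, chiefly magnesium and phosphorus; the number missing should be reported by cohort.
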